APPENDIX VIII

GUIDELINES FOR REPORTING OF ADVERSE EVENTS (AE)/ ADVERSE DRUG REACTIONS (ADR) OCURRING WITH COMMERCIAL AGENTS

1. WITHIN 10 DAYS, SEND TO THE CITY OF HOPE IRB AND DATA SAFETY MONITORING BOARD C/O CPRMC.
 - a) A COPY OF THE FDA FORM 3500
2. IN ADDITION, FOLLOW THE GUIDELINES BELOW

The following guidelines for reporting an AE/ADR apply to this protocol which uses commercial anticancer agents. The following AE/ADR experienced by patients accrued to this protocol and attributed to the commercial agent(s) should be reported:

- (a) Any AE/ADR which is life threatening (Grade 4) or fatal (Grade 5) and unknown.^{1,2,3} Any occurrence of secondary AML or MDS must also be reported.
- (b) Any increased incidence of a known AE/ADR reported in the protocol.
- (c) Any AE/ADR which is fatal (Grade 5), even though known.³

The AE report, documented on Form FDA-3500 should be mailed to the address below within 10 working days:

or Fax to: Medwatch
[name] [name]
[name]

¹ For grading reactions, see App V, VI.

² All known toxicities can be found in either the drug Information, Background or in the consent form sections of the protocol.

³ A report shall be submitted if there is only a reasonable suspicion of drug effect.

Reactions judged definitely not treatment related should not be reported, except that all deaths while on treatment or within 30 days after treatment must be reported. Any death more than 30 days after treatment which is felt to be treatment related must also be reported.

Appendix IX

Eligibility Checklist #99041

Inclusion Criteria (circle yes or No)

1. Subject has acute myelogenous or lymphocytic leukemia who are not in first remission or second remission i.e. after failing remission induction therapy or in relapse or beyond second remission, or patients with chronic myelogenous leukemia in blastic phase of the disease are eligible for the study. Patients with refractory anemia with excess blasts and in transformation will be eligible.

YES NO

2. Subject has a HLA (A,B,C,DR) identical siblings who is willing to donate bone marrow for marrow grafting. All ABO blood group combinations of the donor/recipient are acceptable since even major ABO compatibilities can be dealt with by various techniques.

YES NO

3. A cardiac evaluation with electrocardiogram and MUGA or echocardiogram is required in all subjects and must have an ejection fracture of greater than or equal to 50%.

YES NO

4. Subject is older than 16 and the upper age limit are physiological age of 50.

YES NO

5. Subject has a serum creatinine of less than or equal to 1.2 or creatinine clearance $> 80\text{ml/min}$ and a bilirubin of less than or equal to 1.5. Subjects should also have an SGOT and SGPT less than 5 times the upper limit of normal.

YES NO

6. The time from the last induction or reinduction attempt is greater than or equal to 28 days.

YES NO

7. Signed informed consent form approved by the IRB.

YES NO

8. Pulmonary function tests including DLCO is performed and FEV₁ and DLCO are greater than 50% of predicted normal value.

YES NO

Donors

9. Is sibling donor histocompatible with the prospective recipient?

YES NO

10. Donor does not have psychological or medical reasons and they are able to tolerate the procedure.

YES NO

Are all answers YES?

YES NO

*Note: If all answers have been circled YES then the subject is eligible to go on the study.

Exclusion Criteria

All answers must be NO (circle YES or NO)

11. Prior radiation therapy that will exclude the use of total body irradiation.

NO YES

12. Patients who have undergone bone marrow transplantation previously and who have relapsed.

NO YES

13. Patients with psychological or medical condition that the physician deems unacceptable to proceed to allogeneic bone marrow transplant.

NO YES

Are all answers NO?

YES NO

*Note: If all answers were NO then the subject is eligible for study entry.

*Note: If all the answers are not YES or NO in appropriate sections then go over this case with the PI. If the PI approves an eligibility waiver then the reasons why must be documented in the subject's medical record or research record and a protocol deviation form must be filled out. Per regulatory policy, the PI can only make one waiver of the same criteria without amending the study and getting IRB approval prior to entry.

CRA signature _____ Date ___/___/___

Patient Name: _____ MR# _____

| | YES | NO | DATE / RESULT |
|--|-----|----|---------------|
| CONSENT FORM SIGNED? | | | |
| All questions must be answered "YES" to be eligible. | | | |
| 1. Patient has Acute Myelogenous Leukemia or lymphocytic Leukemia who is not in first remission or second remission, i.e. after failing remission induction therapy or in relapse or beyond second remission, or diagnosed with Chronic Myelogenous Leukemia in blastic phase of the disease is eligible. *Patients with refractory anemia with excess blasts and in transformation will be eligible. | | | |
| 2. Patient has a HLA (A,B,C,DR) identical sibling who is willing to donate bone marrow for marrow grafting. (All ABO blood group combinations of the donor/recipient are acceptable) | | | |
| 3. Ejection fraction of greater than or equal to 50%. | | | |
| 4. Patient is older than 16 and the upper age limit are physiological age of 50. | | | |
| 5. Serum Creatinine of less than or equal to 1.2 or creatinine clearance > 80 ml/min. | | | |
| 6. Bilirubin of less than or equal to 1.5 | | | |
| 7. SGOT and SGPT less than 5 times the ULN | | | |
| 8. The time of the last induction or reinduction attempt is greater than or equal to 28 days. | | | |
| 9. Pulmonary function tests are greater than 50% of predicted normal value. | | | |
| 10. Is the sibling donor histocompatible with the recipient | | | |
| 11. Donor does not have psychological or medical problems and they are able to tolerate the procedure? | | | |
| All answers must be answered "NO" to be eligible. | | | |
| 1. Prior radiation therapy that will exclude the use of total body irradiation. | | | |
| 2. The patient has undergone bone marrow transplantation previously and who have relapsed. | | | |
| 3. Patient with psychological or medical condition that the physician deems unacceptable to proceed to ALLO BMT? | | | |
| 4. Is the patient pregnant or lactating? | | | |
| BASELINE TESTS. All testing must be completed 14 days prior to starting treatment. | | | |
| CBC, DIFF, PLT | | | |
| Complete Chemistry panel | | | |
| Magnesium | | | |
| Hepatitis panel | | | |
| HIV test | | | |
| PT, PTT | | | |
| Urinalysis | | | |
| Pregnancy test | | | |
| 24 hour creatinine clearance | | | |
| CMV | | | |
| HSV/HZV | | | |
| Immunoglobulin level | | | |
| Pulmonary function test | | | |
| EKG | | | |
| Chest x-ray | | | |
| CT Scan of the: | | | |
| a. Chest | | | |
| b. Abdomen | | | |
| ECHO or MUGA | | | |
| Lumbar puncture (see 6.1g for conditions) | | | |
| Bone marrow: * can be done within 4 weeks* | | | |
| a. aspiration | | | |
| b. biopsy | | | |
| c. cytogenetics | | | |

Eligibility completed by (signature & printed): _____

Date completed: _____

After all eligibility has been met, fax this form, the consent form and all outside test results before the patient starts treatment to: [name], CCRA at City of Hope, Dept. of Biostatistics

[contact] [contact] [name]

Eligible: YES / NO

COH CRA SIGNATURE: _____

IRB # 99041 (BU, FTBI, VP-16, BMT)
Eligibility Checklist

Patient Name: _____ MR# _____

| CONSENT FORM SIGNED? | YES | NO | DATE / RESULT |
|--|-----|----|---------------|
| All questions must be answered "YES" to be eligible. | | | |
| 1. Patient has Acute Myelogenous Leukemia or lymphocytic Leukemia who is not in first remission or second remission, i.e. after failing remission induction therapy or in relapse or beyond second remission, or diagnosed with Chronic Myelogenous Leukemia in blastic phase of the disease is eligible. *Patients with refractory anemia with excess blasts and in transformation will be eligible. | | | |
| 2. Patient has a HLA (A,B,C,DR) identical sibling who is willing to donate bone marrow for marrow grafting. (All ABO blood group combinations of the donor/recipient are acceptable) | | | |
| 3. Ejection fraction of greater than or equal to 50%. | | | |
| 4. Patient is older than 16 and the upper age limit are physiological age of 50. | | | |
| 5. Serum Creatinine of less than or equal to 1.2 or creatinine clearance > 80 ml/min. | | | |
| 6. Bilirubin of less than or equal to 1.5 | | | |
| 7. SGOT and SGPT less than 5 times the ULN | | | |
| 8. The time of the last induction or reinduction attempt is greater than or equal to 28 days. | | | |
| 9. Pulmonary function tests are greater than 50% of predicted normal value. | | | |
| 10. Is the sibling donor histocompatible with the recipient | | | |
| 11. Donor does not have psychological or medical problems and they are able to tolerate the procedure? | | | |
| All answers must be answered "NO" to be eligible. | | | |
| 1. Prior radiation therapy that will exclude the use of total body irradiation. | | | |
| 2. The patient has undergone bone marrow transplantation previously and who have relapsed. | | | |
| 3. Patient with psychological or medical condition that the physician deems unacceptable to proceed to ALLO BMT? | | | |
| 4. Is the patient pregnant or lactating? | | | |
| BASELINE TESTS: All testing must be completed 14 days prior to starting treatment. | | | |
| CBC, DIFF, PLT | | | |
| Complete Chemistry panel | | | |
| Magnesium | | | |
| Hepatitis panel | | | |
| HIV test | | | |
| PT, PTT | | | |
| Urinalysis | | | |
| Pregnancy test | | | |
| 24 hour creatinine clearance | | | |
| CMV | | | |
| HSV/HSV | | | |
| Immunoglobulin level | | | |
| Pulmonary function test | | | |
| EKG | | | |
| Chest x-ray | | | |
| CT Scan of the: | | | |
| a. Chest | | | |
| b. Abdomen | | | |
| ECHO or MUGA | | | |
| Lumbar puncture (see 6.1g for conditions) | | | |
| Bone marrow: * can be done within 4 weeks* | | | |
| a. aspiration | | | |
| b. biopsy | | | |
| c. cytogenetics | | | |

Eligibility completed by (signature & printed): _____
Date completed: _____

After all eligibility has been met, fax this form, the consent form and all outside test results before the patient starts treatment

to: [name], CCRA at City of Hope, Dept. of Biostatistics

[contact] [contact] [name]

IRB#: 99041

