1.0 OBJECTIVES

1.1 To determine the efficacy of intravenous busulfan, dose targeted to achieve AUC of 700-900 combined with fractionated total body irradiation and VP16 as a preparative regimen for marrow transplantation from an HLA-identical sibling in patients with advanced hematological malignancies (AML or ALL) beyond 2nd remission, induction failure, in relapse, chronic myelogenous leukemia in blast crisis and myelodysplasia (RAEB and RAEBIT).

Rev. 6/13/02 1.2 To determine the efficacy of this regimen in patients with AML in first remission with unfavorable cytogenetics.

1.3 To evaluate the early and late toxicities of this regimen.

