5.0 ELIGIBILITY CRITERIA

5.1 Inclusion Criteria

- 5.1.1 Patients with acute myelogenous or lymphocytic leukemia who are not in first remission or second remission i.e. after failing remission induction therapy or in relapse or beyond second remission, or patients with chronic myelogenous leukemia in blastic phase of the disease are eligible for the study. Patients with refractory anemia with excess blasts and in transformation will be eligible.
- 5.1.2 All candidates for this study must have a HLA (A,B,C,DR) identical siblings who is willing to donate bone marrow for marrow grafting. All ABO blood group combinations of the donor/recipient are acceptable since even major ABO compatibilities can be dealt with by various techniques. (Red cell exchange or plasma exchange). Peripheral blood stem cells or bone marrow can be used.
- 5.1.3 Prior therapy with VP-16 and busulfan is allowed.
- 5.1.4 Patients must be older than 16 and the upper age limit is physiological age of 50.
- 5.1.5 A cardiac evaluation with electrocardiogram and MUGA or echocardiogram is required in all patients. Patients must have an ejection fracture of greater than or equal to 50%.
- 5.1.6 Patients must have a serum creatinine of less than or equal to 1.2 or creatinine clearance $> 80\text{ml/min}$.
- 5.1.7 A bilirubin of less than or equal to 1.5. Patients should also have an SGOT and SGPT less than 5 times the upper limit of normal.
- 5.1.8 Pulmonary function tests including DLCO will be performed. FEV₁ and DLCO should be greater than 50% of predicted normal value.

5.1.9 The time from the last induction or reinduction attempt should be greater than or equal to 28 days.

5.1.10 Signed informed consent form approved by the IRB is required. The patient, family member and transplant staff physician (physician, nurse, and social worker) meet at least once prior to starting the transplant procedure. During this meeting all pertinent information with respect to risks and benefits to donor and recipient will be presented. Alternative treatment modalities will be discussed. The risks are explained in detail on the enclosed consent forms.

Revised 8/28/00

Revised 3/11/02

Revised 6/13/02

5.1.11 Patients with AML in first remission with poor risk cytogenetics (11q abnormalities, -7,-5, complex abnormalities i.e. > 3 abnormalities, 6;9 translocation and 3q abnormalities del (7q), del (5q), complex abn ≥ abnormalities, 9q, 20q, 21q, 17p, t(9;21)).

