The intent-to-treat group will include all patients receiving the preparative regimen for BMT. For overall survival, failure time will be calculated from the day of first treatment to the day of death due to any cause for those patients who fail. For DFS, the failure time will be calculated from the day of first treatment to the day of disease relapse or death due to any cause. For patients who remain alive and well at the time of analysis, the survival time will be censored as of the date of last contact. The Cox proportional hazard regression model will be used to analyze possible prognostic factors for relapse, DFS and overall survival.

Revised
9/26/00

12.5 Patients with AML with unfavorable cytogenetics will be a subset analysis that will include approximately 12 patients. This number is too small for formal hypothesis testing. It will give us some experience with this population of patients and descriptive analysis will be used along with estimation of relapse rate and 95% C.I.

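### Item 1 of all three eligibility checklists omits the first-remission AML group that 5.1.11 and objective 1.2 admit, so the form gives the wrong eligibility result for these patients

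*Combined protocol and SAP*

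**What the plan says.** Section 1.0 sets out objective 1.2: "To determine the efficacy of this regimen in patients with AML in first remission with unfavorable cytogenetics". Section 5.1 admits the group in 5.1.11: "Patients with AML in first remission with poor risk cytogenetics", followed by a list of qualifying abnormalities. Criterion 5.1.1 covers the advanced-disease group and begins "Patients with acute myelogenous or lymphocytic leukemia who are not in first remission or second remission". It then adds CML in blastic phase and refractory anemia with excess blasts or in transformation. No AML patient can be both outside first remission and in it, so 5.1.11 can only be read as an alternative to 5.1.1.

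Appendix IX contains three checklists. Item 1 of the first reads "Subject has acute myelogenous or lymphocytic leukemia who are not in first remission or second remission". Item 1 of the second and third reads "Patient has Acute Myelogenous Leukemia or lymphocytic Leukemia who is not in first remission or second remission". In each, the remaining routes to YES are the same CML and refractory-anemia categories as in 5.1.1. Every inclusion answer must be YES. If not, the case is reviewed with the principal investigator. A waiver must be documented and a protocol deviation form completed, and "the PI can only make one waiver of the same criteria without amending the study" and obtaining IRB approval.

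Section 12.5 says that AML patients with unfavorable cytogenetics "will be a subset analysis that will include approximately 12 patients", with a descriptive analysis, an estimated relapse rate and a 95% confidence interval.

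**The concern.** The checklist is the working record of eligibility. The second and third copies are to be faxed to the biostatistics department, with the consent form and outside test results, before treatment starts. For patients whom the protocol deliberately added, the form produces a NO.

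Two things are at stake. The first is the eligibility record: an eligible patient is documented as an exception, or item 1 is marked YES when its wording is not met. The second is the subset in 12.5. Its members should be identifiable from what was recorded at entry, and the form has no place to state under which criterion a patient came in.

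**Working it through.** No power or error-rate calculation applies. The check is a comparison of texts, followed by simple proportions.

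**Step 1. Take one patient through both texts.** Suppose AML in first remission with monosomy 7, one of the abnormalities listed in 5.1.11.

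| Test | Section 5.1 | Item 1, all three checklists |
|---|---|---|
| Acute leukemia outside first and second remission | No (5.1.1) | No |
| CML in blastic phase | No (5.1.1) | No |
| Refractory anemia with excess blasts, or in transformation | No (5.1.1) | No |
| AML in first remission, poor-risk cytogenetics | **Yes (5.1.11)** | No such line |
| Result | Eligible | NO |

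The two texts disagree for every patient who enters only through 5.1.11.

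**Step 2. Follow the NO.** The first checklist sends it to the principal investigator. A waiver adds a deviation form. The limit is one waiver of the same criterion without an amendment and IRB approval, so waivers are not a route for a planned group of patients.

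**Step 3. Size of the group.** Inputs: approximately 12 patients (12.5) and 50 patients (12.2). The documents do not settle two things. Section 12.5 does not mention first remission, so treating the 12 as the 5.1.11 group is an assumption, supported by objective 1.2 and 5.1.11. Section 12.2 describes the 50 as having advanced malignancies, so it is unclear whether the 12 are among them.

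- Within the 50: 12/50 = 24%.
- In addition to the 50: 12/(50 + 12) = 12/62 = 19%.

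**Step 4. What the form records about cytogenetics.** The second and third checklists list cytogenetics under the baseline bone marrow tests, in a table with a date/result column. The first has no such line. No item in any copy asks whether the result meets 5.1.11.

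**Step 5. Why clean membership matters in a subset this small.** With 12 patients, one relapse moves the estimated rate by 1/12 = 8.3 percentage points. At 5 relapses of 12 (42%, near the 40% that Section 2.0 gives for the existing regimen), the exact 95% interval is 15% to 72%.

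**The case against.** The strongest reply is that Section 5.0 governs and Appendix IX is a form that lagged behind revisions. Section 13.0 says that the only exclusions are those in Section 5.0, which contains 5.1.11. A NO on the form does not bar entry: it prompts a discussion with the investigator, who would find 5.1.11. Objective 1.2 is itself marked as a revision, so the protocol has already been changed to admit this group, and a patient who meets 5.1.11 arguably needs no waiver. The first checklist also omits pregnancy, which 5.2.4 excludes, and this too suggests an outdated form.

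Most of this stands, and it rules out three stronger readings.

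- A reader might infer that the form shuts out the whole group, or that 12 minus one waiver leaves 11 ineligible. That requires the form to outrank Section 5.0, and Section 13.0 points the other way.
- A reader might infer that the form never records cytogenetics. Two copies do have the baseline line. What is missing is a question tied to 5.1.11.
- A reader might take 24% as the affected share. It holds only if the 12 are the first-remission group and lie within the 50.

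The reply does not remove the contradiction. Section 13.0 shows which text should prevail but does not correct the form. Staff completing it must still mark item 1 contrary to its wording or treat an eligible patient as an exception.

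**Conclusion.** The inconsistency is real and stands in the current text: three checklists, one missing alternative in each. For a patient who enters through 5.1.11, the form gives a result that contradicts Section 5.0. The likely effect is wrong waiver and deviation records and no entry-level marker of cohort. The documents do not support predicting that enrolment of this group would fail.

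The group is about 12 patients, or 19% to 24% of the trial, on the assumption that the subset in 12.5 is the first-remission group. The textual contradiction does not depend on that assumption; only its size does. No analysis method, sample size or stopping rule is affected. The point is modest but more than clerical, and it should be corrected.

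**What to change.** In every copy of the Appendix IX checklist, reword item 1 so that it is answered YES if the patient meets 5.1.1 or meets 5.1.11, and add a tick for which of the two was met. The tick identifies the cohort at entry and ties the baseline cytogenetics result to the criterion it has to satisfy.

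The cost is a form revision. Eligibility as written in Section 5.0, the tests performed, the number of patients and the analyses all stay the same.

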APPENDIX X

Time points to grade toxicities and collect data.

Day 30 after PBSCT/BMT CTC form.

Day 31 – 100 CTC form and IBMTR booklet.

101 – 365 LT Follow up form.

Every year LT follow up form.
